## Research Protocol

### Title: Pair 2 Care: Peer Support for Caregivers of African Americans Living with Dementia

#### I. Objective

The purpose of this study is to test a peer support intervention for family caregivers who are caring for a loved one living with dementia. Peer Support for Caregivers of African Americans Living with Dementia (Pair 2 Care) is a co-created culturally sensitive family caregiver peer support intervention. We will determine if Pair 2 Care is feasible and acceptable by evaluating eligibility criteria, recruitment and retention data, protocol adherence, satisfaction, and feedback on appropriateness of the intervention for broader dissemination. At 6 months as compared to baseline, current family caregivers will report less anxiety and depression, higher quality of life, perceived social support, and self-efficacy for surrogate decision making as well as intent to use palliative care or hospice services as part of advance care planning and healthcare decision making for their care recipient living with dementia.

Throughout this protocol the terms 'caregivers' or 'family caregivers' will be used interchangeably to refer to family caregiver participants. Unless otherwise specified, both terms will be used to reference current and former family caregiver participants. Former family caregivers are 'mentors' and current family caregivers are 'mentees' and they referred to as such throughout this proposal. Study participants are current family caregivers (mentees) and former family caregivers (mentors). No professional, hired, formal caregivers such as nurses, physicians, and nursing assistants are included in the study. The terms Black and African American are also used interchangeably to represent Blacks residing in the US who are descendants of Sub-Saharan Africa.

#### II. Background and Rationale

African Americans are twice as likely to develop Alzheimer's disease and related dementias (ADRD) than their White counterparts. These individuals are, however, more often diagnosed later, creating additional physical, spiritual, psychosocial challenges for both the person living with ADRD and their family caregivers. African American ADRD family caregivers are therefore at greater risk for adverse physiological and psychological health effects of family caregiving, including significant burden and stress. Evidence suggests that peer to peer support using storytelling may be effective in assisting ADRD caregivers with surrogate healthcare decision making, an important aspect of palliative care. Access to and use of palliative care, a recognized approach to serious illness care symptom management, among African Americans are low. The impact of this healthcare inequity further reduces the quality of life for African American ADRD family caregivers and subsequently their care recipients.

Prior approaches to serious illness care have failed to address the needs of African Americans living with ADRD from a palliative care perspective. This inability to meet their needs leads to increased unmet caregiver needs. Peer mentorship, a relationship-centered person-to-person approach may reduce healthcare decision making burden within cultural groups such as African Americans through cultural tailoring by promoting oral traditions, personal contact, and storytelling. Our previous study included perspectives of lower socioeconomic status African American ADRD caregivers who have expressed the need for person-centered, non-judgmental, on-demand, culturally congruent caregiving support for advance care planning and healthcare decision making. Simultaneously, our former family caregivers retrospectively described

perceived benefits of peer support while caregiving and their willingness to serve as peer mentors to current family caregivers. Additional data from healthcare provider and community stakeholders support the need and potential benefits of peer support for ADRD caregivers. Based on these preliminary findings, there is an urgent need and exciting opportunity to address the unmet palliative care needs of current caregivers through peer support. For this innovative study, we will use the experiential expertise of former family caregivers as mentors to help current family caregivers as mentees with advance care planning and healthcare decision making. The purpose of this study is to test a peer support intervention for family caregivers who are caring for a loved one living with dementia. Peer Support for Caregivers of African Americans Living with Dementia (Pair 2 Care) is a co-created culturally sensitive caregiver peer support intervention. The following specific aims will be addressed:

[figure not shown]
**Aim 1:** Conduct feasibility and acceptability testing of Pair 2 Care in current ( $n=15$ ) and trained former ( $n=15$ ) African American ADRD family caregiver peers paired based on congruent identity traits (e.g., relationship to care recipient, gender identity, etc.). We will determine if Pair 2 Care is feasible and acceptable by evaluating eligibility criteria, recruitment and retention data, protocol adherence, satisfaction, and feedback on appropriateness of the intervention for broader dissemination.

**Aim 2:** Assess preliminary intervention outcomes of caregiver anxiety, depression, quality of life, social support, self-efficacy for surrogate decision making, and intent to use palliative care or hospice services to determine potential effectiveness of the Pair 2 Care Intervention. At 6 months as compared to baseline, current caregivers (mentees) will report less anxiety and depression, higher quality of life, perceived social support, and self-efficacy for surrogate decision making as well as intent to use palliative care or hospice services as part of advance care planning and healthcare decision making.

African Americans are at high risk for developing ADRD and, thus, to experience the negative impacts of ADRD caregiving. African Americans are twice as likely to develop ADRD as compared to Whites. Caregiving for older adults living with ADRD is complex. A lack of personal time, socialization opportunities, and ADRD stigma results in caregiver isolation. Therefore, these African American ADRD caregivers may face significantly more caregiver stress, physical, and psychological effects as compared to other caregivers.

Access and use of palliative care is low among African Americans. Much of the focus on palliative care for African Americans is on cancer and other serious illnesses. However, there is a lack of data on the use of palliative care in African Americans living with ADRD. Alzheimer's disease and related dementias are a set of serious, life limiting illnesses where both the person living with ADRD, and their family caregiver(s) can greatly benefit from palliative care. Yet, African Americans are less likely to have access to or receive palliative care than other racial/ethnic groups.

Evidence-based caregiver support interventions are lacking and therefore often do not meet the needs of African American ADRD caregivers in a culturally sensitive manner. Interventions that provide support for the persons living with other chronic diseases such as cancer are more widely available than those available for ADRD caregivers. While support groups are shown to be beneficial, they are often rigid with inflexible meeting times, locations, topics covered, etc. Similar to the term 'dementia,' 'support groups' may have negative connotations among African Americans. Although serious illness caregiving can be similar, the nature of ADRD caregiving differs primarily because of the associated cognitive decline and behavioral symptoms.

Family caregiver peer support as a potential adjunct to palliative for African American ADRD caregivers. Peer support interventions can help to support caregivers with care recipient behavioral, psychological, and other symptoms of ADRD and also improve caregiver quality of life. Lay (social) and professional (healthcare provider) support are important and integral to health promotion. Supportive social relationships include both embedded (i.e. family, friends, church members, neighbors) and created social networks. These self-help support networks may be in group form or one-to-one involvement as well as paraprofessional (involving extensive training and professional involvement).

involvement). The former involves peer relationships, a provision of peer support. Peer support is an established concept and social relationships such as for family caregivers providing care for a loved one living with ADRD are important for health and wellbeing promotion. Peer support has also been established as supportive for transitional stressors such as bereavement and for situational stressors as well as health promotion. Peer support has been previously used for individuals who have experienced significant loss. For example, among African Americans receiving long-term dialysis, peer mentoring has resulted in an increase in advance directive discussions and advance directive completion, improving anxiety and overall quality of life.

This study is novel because it combines cultural tailoring with the concept of peer support to meet the unique needs of African American ADRD caregivers. Our Pair 2 Care caregiver support intervention poses a highly innovative strategy that has the potential to address advance care planning and healthcare decision making, a significant health disparity problem and thereby promote health equity. It includes the flexibility needed for African American ADRD caregivers. Our innovative approach will advance the field toward improving ADRD caregiving outcomes. The Pair 2 Care model has potential for adaptation to meet the needs of caregivers of persons living with other diseases and/or racial/ethnic populations in the future. It is responsive to the National Alzheimer's Plan and request for proposals from professional organizations such as the Hospice and Palliative Nurses Association and the American Academy of Hospice and Palliative Medicine. This progress places significant focus on equity in palliative care.

**Preliminary Work.** Our prior work as well as that of others have shown that perceived understanding of end-of-life terminology in health-related decision-making matters and that cultural tailoring is critical to improving advance care planning approaches. By using a multistakeholder approach, we have found that access to culturally-specific mechanisms is an unmet need to improve advance care planning and healthcare decision making engagement (see Figure 1). Factors such as shared understanding, identity, and experiences through storytelling are consistent with embracing cultural affinity in the African American community.

Figure 1 depicts our Current Family Caregiver Community Research (FamCare) Study approach which included perspectives from former family caregivers, healthcare providers, and community leaders to identify the healthcare decision making needs of those who are currently caregiving. This foundational work was guided by the Model to Explain Factors Impacting Advance Care Planning Among African Americans developed by Sanders et al (2016), including the

development of interview guides. This model describes personal, intrapersonal, and structural barriers to advance care planning and healthcare decision making and stresses the likelihood of informal discussions instead of documented plans among African Americans. Cultural affinity is similar to social identity, which is defined as one's emotional closeness to and in-group identification to a specific sub-culture. The family caregivers in our previous FamCare study expressed a strong desire for advance care planning and healthcare decision making to be more aligned with cultural affinity for easier adoption, to match patients' needs and wishes, and improve completion. In this proposed study, we will also leverage the desire of former family caregivers to 'give back'. We will, therefore, use our existing participant cohort of former family caregivers for this proposed study. This approach promotes trust and continued engagement in research for a group already at high risk for low research participation.

Pair 2 Care is a low-cost intervention that maximizes flexibility for peer connections using technology. Available financial assistance for reduced Wi-Fi cost may be recommended for family caregivers who request Wi-Fi access. In the future, the Pair 2 Care framework can be implemented into existing programs such as African American Alzheimer's and Wellness Association (AAAWA) and the Alzheimer's Association and scaled for adaptation to other caregiver types and racial/ethnic groups ensures sustainability. Future policy development will ensure its inclusion in national caregiver programs.

While there are no direct benefits to the individual study participants, the proposed study will be highly important in filling gaps in essential information that will lead to improved interventions and policy changes. It will provide feasibility and acceptability pilot data with this initial intervention testing to support efficacy testing.

### **III. Procedures**

#### **Overall Procedures**

All study procedures will be approved by The Ohio State University (OSU) Institutional Review Board (IRB). Procedures will be conducted remotely allowing flexibility for participation. Intervention development initially began using stakeholder data collected from our FamCare Study as previously described. A total of 15 people who are currently caring for a loved one (current caregivers) and total of 15 people who cared for a loved one who lived with dementia (former caregivers) will be enrolled in the Pair 2 Care research study. Mentors may be assigned an additional mentee. Former caregivers (mentors) will complete up to two 1-hour training sessions to become mentors to current caregivers (mentees). Former caregivers will be called mentors and current caregivers will be called mentees. Each mentor and mentee will be paired for 6 months for peer support. We will attempt to select mentors and mentees for pairing based on something they have in common as identified using the (see Participant Intake Form). During the Pair 2 Care program/intervention, mentors will provide non-judgmental, flexible, culturally sensitive support to their mentees and share their personal caregiving experiences. This may include information such as the following: accessing/selecting healthcare providers, attending doctor visits, attending worship services, coronavirus pandemic/endemic, exercise, faith, family dynamics, finances, healthcare decision making, mental health, nutrition, physical health, sleep, social activities, spirituality. Data collected during the participant screening process such as family caregiver type, etc., may be used from consented individuals. Once each week during the 6 months connection, mentees will be sent a short survey (see Appendix for Weekly Mentee Interaction Assessment Response Form) by text, email, and/or phone call to complete about their interaction with their mentor during the last week. If not completed by the mentee, a text email

and/or phone call reminder will be sent within a couple days after as a reminder to complete it. A weekly text/email/reminder phone call message may be used to: 1) thank participants for being in the study, 2) remind mentees and mentors to connect, and or 3) remind mentees to complete their Weekly Mentee Interaction Assessment Response Form.

### **A. Research Design**

Design. A community-based participatory approach will be used to further develop and pilot test Pair 2 Care. The proposed intervention was initially developed based on data provided by stakeholder participants from the principal investigator's (PI) completed studies (Decision Making for African American with Dementia Study - DAADS and FamCare Study).

Community Advisory Board - FamCAB. The Family Caregiver Community Research (FamCare) Lab Community Advisory Board Community Advisory Board (FamCAB) has been formed. The FamCAB members are not part of the research and therefore are not research study participants. However, their engaged work is informing this and other research within the PI's research program. As non-research participants, the overall goal of the FamCAB is to assist in tailoring the Pair 2 Care intervention to meet the needs of the current caregiver mentee participants and provide recommendations for problem-solving and promote equity by meeting the needs of African American ADRD caregivers and for intervention sustainability over time. The purpose of the FamCAB will be to: 1) assist the study team with accessing potential caregiver participants in the local community, 2) introduce study staff to key community leaders and members, 3) identify community assets (e.g., resources, organizations) to support the proposed study, 4) develop the protocol and ensure content validity by reviewing the preliminary Pair 2 Care study protocol (including mentor training and materials) prior to participant enrollment, and 5) provide iterative feedback on intervention development before, during, and after pilot testing the intervention to help ensure acceptability and usability. The FamCAB will advise the research team on study procedures (e.g., discussion topics, frequency of interactions, etc.). As the FamCAB will not access data or participant identifying information.

See Figure 2 for intervention development process. The FamCAB will help to ensure goals for this community-engaged study efforts are met and will be partners in the development and testing of the intervention even beyond the proposed study. For the Pair 2 Care Study, the mentors and mentees will be brought together for peer support. Both qualitative and quantitative data will be collected. Various types of data will be collected from mentors and mentee at baseline, pre-, intra, and post intervention to pilot test Pair 2 Care for this Stage I intervention study.

## B. Sample and Setting

A sample of  $n=15$  current family caregivers (mentees) and  $n=15$  former family caregivers (mentors) who self-identify as being Black/African American caregiver of an older adult living with or who lived with ADRD will be recruited to pilot test the Pair 2 Care program/intervention. For this short duration study, participants will be recruited from the Central Ohio area – Columbus area and surrounding communities. As requested by our prior study participants for this co-created intervention, this study is being conducted virtually. While recruitment may occur via phone, video call, email, or in-person using the IRB-approved study flier and recruitment scripts, consenting and data collection will be completed remotely. Therefore, participants (mentors and mentees) are not required to meet in-person for this study.

[figure not shown]

```
graph TD; A[Ongoing CAB A] --> B[6-month caregiver intervention]; B --> C[1-month follow-up]
```

## C. Recruitment

Potential participants will be recruited from the Central Ohio area – Columbus area and surrounding communities through research registries, community partnerships and events such as health fairs and at churches, snowball methods, and social media. For this remotely conducted study, all study-related materials will be organized online from the PI's College of Nursing office or the remote work site of the research team members. Research team members may work in-person at The Ohio State University or remotely. If recruiting remotely (as with data collection), research team members will ensure that they are located in a private location and their computer is connected to the CON remote access VPN to ensure security. Headsets will be used as needed to help to ensure privacy of conversations. No participant information will be stored at research team members' remote locations. All electronic study data will be stored on a secure OSU College of Nursing research server or in Research Electronic Data Capture (REDCap). This includes demographic and other survey data as well as interview audio and transcripts. Each participant will be assigned a unique study identification alpha-numeric code. Only members of the study team will be able to link participants with study identification alpha-numeric code. Names, phone numbers, and mailing addresses will be stored separately from study alpha-numeric code numbers, verbal consents, study data, and interview transcripts. Data collected as part of this study will be stored in an established data repository per The OSU Policy and Procedures. The participants will be able to choose the location they make phone, or video call or email from for interacting with study team members.

Figure 2: Program Development Process

The Recruitment Script (see appendix) will be used for phone, video call, email, or in-person recruitment along with the study flier (see appendix). Community-based organizations such as nursing homes, churches, and dementia-focused organizations may share study fliers with potential participants such as through email via listservs, posting on their organization social media sites, or posting study fliers within their organizations using the Community Partner Recruitment (via email, phone, video call, or in-person) along with the study flier. The FamCare Lab Website will have a page dedicated to the Pair 2 Care Study that will include the study flier, Study Introduction Note, and the Study Welcome Video (see script in appendix). The Study Welcome Video will also be placed on the lab website's home page. Potential participants or community partners may choose to share the study flier with others in their contacts, and they may post the flier on their social media sites e.g., Facebook®, Twitter®, and Instagram®. Additionally, the PI and study team members may give caregiving presentations in the community as requested, attend health fairs, such as at nursing homes or other community-based organizations that may include sharing the study flier and offering continuing education credits as needed. These community presentations are educational presentations that the PI conducts as part of her citizenship in the local community based on her expertise. These presentations are given regularly on topics such as palliative and end-of-life care, family caregiving, and dementia, etc. as requested by community-based organizations. Following such community engagements, the IRB-approved study flier may be made available to attendees as with distribution at local health fairs. There will be no additional study information included in the presentations. Snowball methods will also be used for recruitment of study participants. Potential participants will contact the research team either in-person, via phone call, or email for additional study information, and eligibility screening. This convenience sampling approach will be augmented with snowball recruitment methods to identify additional potentially eligible caregiver study participants. Additionally, enrolled participants will also be asked if they know of anyone else who may qualify to participate in the study. If so, the participant will either pass along the study information and PI contact information and potential participant themselves will contact the PI if interested to facilitate snowball recruitment methods. Otherwise, if the participant agrees to reach out to other potential caregiver(s) to ask if it is okay to share their contact information with the study team, the PI or a member of the research team will contact the potential participant to provide study information and determine eligibility using the Caregiver Recruitment Script followed by the Caregiver Screening Form (see appendix).

Recruitment efforts will ensure that each current family caregiver as mentee will be paired with a former caregiver mentor. Participants will also be recruited from FamCare Lab Participant Registry and Website. We will build on established research partnership with current and former family caregivers who previously participated, provided input and feedback, and indicated willingness to be included in future research studies. From our FamCare Study, current and former caregivers expressed their desire to be recontacted to be in research studies as indicated via the prior consent processes. Therefore, they are willing to be recontacted to be screened (using the Screening Form) and invited to participate in this Pair 2 Care study. The following criteria will be used to determine family caregiver participant eligibility:

**Inclusion Criteria:** Current and former family caregivers will be included if they are: 1) at least 18 years old, 2) self-identify as being African American/Black, 3) either currently provide or manage care for at least 8 hours per week for an African American/Black older adult (60 years or older) family member or otherwise fictive kin living with ADRD or did so in the past (at least 6 months post care recipient death). Former family caregivers will be assessed for readiness to be a mentor, including comfort discussing grief and loss. They must indicate that they have experience with palliative care and/or hospice services.

**Exclusion Criteria:** Current and former family caregivers will be excluded if they state that they: 1) do not have this experience, or 2) are uncomfortable discussing healthcare decisions, end-of-life decision making, grief, loss, death, and dying, particularly as it relates to the loss of their loved one who lived with ADRD.

During screening potential participants will be asked if they have access to a Wi-Fi-enabled smart phone or table for use during the study. If they respond 'No', the research team member will provide information for accessing a study-provided Wi-Fi-enabled tablet for study use.

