**Measurement / Instrumentation:** Demographic data (e.g., age, gender, caregiving relationship) will be collected from all caregivers using the respective mentor and mentee demographic form (see appendix). State anxiety (Spielberger State Anxiety Inventory - STAI-S), depression (Center for Epidemiological Studies – Depression - CES-D), quality-of-life (Caregiver-Targeted Quality of Life – CGQOL), self-efficacy for surrogate decision making (Surrogate Decision Making Self-Efficacy Scale - SDM-SES), social support (Medical Outcomes Study Social Support Survey – MOS SSS), and intent to use palliative care/hospice (Mentee Palliative and Hospice Care Intent Form) data will be collected from mentees. Care recipient dementia stage (Quick Dementia Rating System - QDRS) and behavioral and psychological ADRD symptoms (Neuropsychiatric Inventory Questionnaire - NPI-Q) data will also be collected (see Table 3) (see appendix). Audio-recorded interviews (using the Mentee or Mentor Interview Guide – see appendices) conducted at one-month follow up via Zoom®, phone, or other virtual format with participants will characterize their experiences. Mentors will have the option to complete the interview at Month 6 or 7. Mentees will complete the interview at Month 7 (1 Month follow-up). Interviews will be conducted with participants to gather in-depth data on their Pair 2 Care Intervention experiences, including feedback on the likelihood of the intervention meeting the needs of African American ADRD caregivers. A member of the research team will connect with

former caregivers at the 3- and 6-month timeframe for feedback on how the mentoring process is going.

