## K. Data Analysis

Descriptive statistics will be conducted on all participant demographic data using SPSS® or similar software.

Aim 1: Feasibility and acceptability of the Pair 2 Care Intervention in current ( $n=15$ ) and trained former ( $n=15$ ) African American ADRD family caregivers will be determined by our eligibility criteria, recruitment, and retention data (e.g., consent, drop out, refusal rates), protocol adherence, satisfaction, and appropriateness of the intervention for broader dissemination. We will conduct descriptive statistics for this Aim using proportion for categorical measures (recruitment, retention, and protocol adherence) and mean±standard deviation for continuous measures (80% satisfaction and 80% appropriateness). Interviews will be conducted with current caregivers to gather in-depth data on their Pair 2 Care Intervention experiences, including feedback on the likelihood of the intervention meeting the needs of African American ADRD caregivers. Interviews will be analyzed as described below. Aim 2: Descriptive statistics will be used to summarize sample characteristics and outcome measures (anxiety, depression, quality of life, social support, self-efficacy for surrogate decision making, and intent to use palliative care/hospice services) at each time point. For each outcome, we will use mixed-effects linear modeling for repeated measures to model the outcome as a linear function of fixed-effect of time. The model will also include subject-specific random intercepts to adjust for within-subject clustering from repeated measures. We hypothesize that at 6 months as compared to baseline, current caregivers will report less anxiety and depression, higher quality of life, higher social support, higher self-efficacy for surrogate decision making, and higher intent to use palliative care/hospice services. From the mixed-effects modeling, we will test this hypothesis by deriving contrast estimate of change of outcome between baseline and 6 months.

Power analysis suggested that our sample size ( $n=15$ ) will have only 38% power to detect a medium effect size of Cohen's  $d = 0.5$  for outcome change from baseline at 6 months. This effect size is equivalent to a clinical meaningful difference. Therefore, we will not rely on statistical significance. Instead, results interpretation will be guide by point estimates, precision of the estimates (e.g., 95% confidence interval), effect sizes, and their clinical significance.

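### Exclusion 1 extends to current caregivers a palliative or hospice experience requirement that the inclusion criteria place on former caregivers only

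*Combined protocol and SAP*

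**What the plan says.** The inclusion paragraph in III.C opens with three criteria shared by both groups: age, self-identified race, and at least 8 hours a week of care, now or in the past, for an older African American/Black relative or fictive kin with dementia. It then turns to mentors: "Former family caregivers will be assessed for readiness to be a mentor, including comfort discussing grief and loss". The next sentence reads: "They must indicate that they have experience with palliative care and/or hospice services".

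The exclusion paragraph follows at once: "Current and former family caregivers will be excluded if they state that they: 1) do not have this experience". Its second item concerns discomfort in talking about health decisions, death and loss.

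Three other places bear on this:

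- I. Objective defines former caregivers as mentors and current caregivers as mentees.
- II. Background and Rationale justifies the study partly on the ground that "Access and use of palliative care is low among African Americans".
- K. Data Analysis hypothesises that at 6 months, compared with baseline, current caregivers will report "higher intent to use palliative care/hospice services". G. Data Collection says that intent is collected from mentees.

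**The concern.** The two paragraphs give different answers about the same person. A current caregiver with no palliative or hospice experience is eligible under the first and, on the natural reading, ineligible under the second. These are the criteria that decide who enters the study, so staff need one answer.

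Two things are at stake. If the exclusion is applied as written, every mentee will already have met the services whose uptake the study hopes to encourage, and caregivers new to them will be missing from the intent data. Separately, Aim 1 evaluates the eligibility criteria themselves. Table 4 asks that they allow the enrolment target to be reached, with all participants enrolled in Year 1. A shortfall caused by a misworded exclusion could be mistaken for a finding about feasibility. If staff resolve the wording differently from one call to the next, the screening and refusal counts would mix two rules.

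**Working it through.** The plan states no figure on this point, so the check is textual.

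1. **Who must have the experience under the inclusion paragraph?** The sentence "They must indicate that they have experience with palliative care and/or hospice services" begins with a pronoun. Its antecedent is the subject of the sentence before it, former caregivers being assessed as mentors. The requirement therefore falls on mentors only.

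2. **What does the exclusion refer back to?** The phrase in item 1 is not defined there. Within the criteria the word experience has been used once before, in the sentence immediately preceding, where it means palliative or hospice experience. Inclusion criterion 3, on providing care, does not use the word.

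3. **Whom does the exclusion cover?** It names both groups. Nothing elsewhere in the supplied text limits item 1 to mentors.

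4. **Test case.** Take an adult current caregiver who self-identifies as African American/Black, gives at least 8 hours of care a week to an eligible relative with dementia, is comfortable with the discussion topics, and has no palliative or hospice experience.

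| Rule | Experience means palliative/hospice | Experience means caregiving |
|---|---|---|
| Inclusion 1 to 3 | met | met |
| Mentor readiness and experience | does not apply | does not apply |
| Exclusion 2 | not triggered | not triggered |
| Exclusion 1 | **triggered** | not triggered |
| Result | excluded | eligible |

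Eligibility turns entirely on how two undefined words are read, and the reading with the closer antecedent excludes the person.

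5. **Can the effect on recruitment be sized?** If a share *p* of otherwise eligible current caregivers had the experience, filling 15 mentee places would take about 15/*p* such people. The documents describe use as low but give no value of *p*, so the expression has no numerical answer here.

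6. **Can the effect on intent be sized?** That would need the intent form's scale and the baseline scores of experienced and inexperienced mentees. Neither is in the supplied text.

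**The case against.** The strongest reply is that the phrase may mean caregiving experience. The exclusion's subject repeats the opening subject of the inclusion paragraph, where the shared requirement is having given care. On that reading no mentee is lost. One cannot dismiss it merely as redundant with inclusion 3, because for mentors the palliative reading also repeats an inclusion sentence, and exclusion 2 largely repeats the readiness check. This stands as a possible reading. It remains the weaker one, since it passes over the adjacent sentence that uses the word, and a criterion open to both readings still needs repair.

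It can also be said that this is a drafting slip. Exclusion 2 speaks of the loss of a loved one who had dementia, which fits former caregivers and suggests the block was written with mentors in mind. That is probably right. A reader might infer that the sponsor chose to restrict mentees to people with prior experience; the inclusion paragraph points the other way.

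Nor can one say that such caregivers are in fact being turned away. D. Screening relies on the Caregiver Screening Form, which is in an appendix not supplied and may already apply the rule to mentors only.

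Three further inferences go beyond the documents:

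- **A recruitment multiple.** Any such number would rest on an assumed rate of prior experience.
- **A ceiling on intent.** Prior experience may have been brief, unfavourable or with another relative, and need not mean high intent.
- **That the intent hypothesis is about inexperienced mentees.** It covers all mentees. Those without experience may have the most room to change, but they are not the whole target.

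Finally, intent is one of six preliminary outcomes in a pilot that does not rely on statistical significance. That limits the consequence for Aim 2. It does not help Aim 1, where the criteria are under evaluation.

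**Conclusion.** The text is wrong as written and should be corrected. The inclusion paragraph confines palliative or hospice experience to former caregivers. Exclusion 1, on its most natural reading, extends it to current caregivers and so removes mentees who satisfy everything else asked of them. That conflicts with the stated rationale and with the intent hypothesis. It could also slow enrolment of the 15 mentees and make the Table 4 eligibility result hard to interpret.

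The conclusion rests on taking the adjacent sentence as the antecedent, and on the absence of any limiting text elsewhere in what was supplied. No size can be attached to it. Harm to recruitment and compression of the intent scores are possibilities that follow only if the rule is enforced literally.

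**What to change.** Reconcile the two paragraphs:

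- Reword exclusion 1 so that it names both the group and the experience, for example: *former family caregivers who say they have had no experience of palliative care or hospice*. Keep exclusion 2 as a separate item with its own stated group.
- Add a sentence saying that such experience is not required of current caregivers.
- Check that the Caregiver Screening Form says the same, and change it only if it does not.

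Recording prior palliative or hospice experience for mentees at baseline would help describe the intent results, but with 15 mentees it is optional and not part of the correction.

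The cost is a minor amendment to a short piece of protocol text and a check of one form. It adds no participants or visits and leaves the planned analysis unchanged.
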